2.2 Secondary objectives

- a. To compare muscle function/strength at baseline, and 1 and 6 months after commencing Tofacitinib.
- b. To compare muscle biochemistry at baseline, and 1 and 6 months after commencing Tofacitinib.
- c. To seek histological and molecular changes in muscle that relate to changes seen in muscle bulk, biochemistry or function (e.g. hyperplasia or hypertrophy of muscle fibres; or molecular changes relating to activation of anabolic or down-regulation of catabolic pathways).
- d. To relate changes in serum biochemistry (serum creatinine, serum creatine kinase) to biochemical, structural, functional and histological/molecular changes in muscle.
- e. To relate any changes noted in muscle to reduction in systemic inflammation.
- f. To seek any overall changes in body composition.

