2.4 Exploratory endpoint/outcome

- a. Serum cystatin C and myoglobin at baseline, 1 month and 6 months
- b. Percentage change in STAT1/3 phosphorylation of PBMC subset(s) when stimulated with interleukin-6 (IL-6) alone as well as in the presence of tofacitinib – at baseline and at 1 month – and the predictive utility of readout(s) with respect to clinical response to tofacitinib.
- c. Percentage change in fat fraction of upper and lower leg muscle compartments at baseline, 1 month and 6 months. If no difference is observed in this global measure, percentage changes in specific muscle groups (such as quadriceps and hamstrings) may also be measured.

In each case, individual patient data (intra-patient) and pooled group data will be examined, to allow for expected heterogeneity in response.

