9.1 Sample Size

With a sample size of N=15 patients we should be able to detect changes of around the same order of magnitude as the variability in those differences (delta/sigma=1) with greater than 90% power on a one-sided test at the 5% level of statistical significance.

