9.2 Primary Endpoint Analysis

The MRI studies will provide continuous data for the muscle volume (in cm³) of both legs. There will be two volume measurements, one for the lower leg and one for the upper legs at the three timepoints. There will be one spectroscopic measurement which is the ratio of creatine to water in the soleus for all three time points. There are therefore three outcome measures at three time points for each of 15 individuals.

Each outcome measure will be tested for suitability for a one-way repeated ANOVA assessment (checks for outliers, normality, homogeneity and sphericity). If the ANOVA is significant, post-hoc testing will be carried out using Bonferroni correction to identify which timepoints are significantly different. Effect sizes will be calculated.

In the event that the data do not satisfy the criteria for one-way repeated ANOVA, then Friedman's ANOVA will be performed, followed by step-wise post-hoc tests to identify which timepoints are significantly different. Effect sizes will be calculated. All statistics will be performed using IBM SPSS Statistics 24.

Should we establish significant changes in both muscle volume and creatine/water ratio, then we will further investigate the relationship between these changes, bearing in mind the size of this pilot study.

10 Ethics & Regulatory Issues

The conduct of this trial will be in accordance with the ethical principles for medical research involving human subjects determined by the World Medical Association Declaration of Helsinki of the 64th General Assembly in October 2013. All members of the research team and the investigators will be trained in the statutory instrument and those aspects of Good Clinical Practice appropriate to their role in the trial. Favourable ethical opinion and Clinical Trial Authorisation from relevant Competent Authority(ies) will be sought prior to commencement of the trial. Local approvals will be sought before recruitment may commence at each site. Information sheets will be provided to all eligible subjects and written informed consent obtained prior to any trial procedures

11 Confidentiality

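### Section 9.2 examines the link between muscle volume change and creatine/water change only if both changes are significant; it should be estimated whatever those tests show.

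*Protocol*

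**What the plan says.** Protocol section 9.2 names three outcome measures: upper-leg muscle volume, lower-leg muscle volume, and the creatine-to-water ratio in the soleus. All are measured at three visits: "There are therefore three outcome measures at three time points for each of 15 individuals". Each goes into a one-way repeated-measures ANOVA with Bonferroni post-hoc tests, or Friedman's test as a fallback. The section then closes with a conditional analysis: "Should we establish significant changes in both muscle volume and creatine/water ratio, then we will further investigate the relationship between these changes", with the caveat "bearing in mind the size of this pilot study". No other section plans this particular analysis without the condition.

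Two other places bear on it. The closing sentence of section 2.4 (Exploratory endpoint/outcome) says that "individual patient data (intra-patient) and pooled group data will be examined, to allow for expected heterogeneity in response". Section 2.2 (Secondary objectives), items c to e, relates muscle findings to histology, serum biochemistry and inflammation, for example "To relate any changes noted in muscle to reduction in systemic inflammation", with no significance condition attached.

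**The concern.** A significant average change in each measure is neither necessary nor sufficient for the individual changes to be related. If some patients gain on both measures and others lose on both, the changes are strongly related while the averages sit near zero. If every patient gains about the same amount on both, both averages are significant and there may be no relationship at all. The condition therefore screens on the wrong quantity.

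It also makes reporting depend on the results: the link appears only in data sets that happened to show two significant averages. A study meant to inform a later controlled trial is better served by an estimate that is always reported.

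The condition is also not fully defined. Section 9.2 has two volumes and two layers of testing, and does not say which volume must change or whether the overall ANOVA or a post-hoc contrast decides.

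**Working it through.** **Inputs from the protocol.** N=15, a detectable effect of delta/sigma=1 (sigma being the SD of the differences), one-sided 5%, power above 90% (section 9.1); three visits and one repeated-measures ANOVA per measure (section 9.2).

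**Assumptions, since the protocol is silent.** ANOVA level 5%; spherical errors; SD of the baseline-to-6-month change set to 1, so the error variance at each visit is 0.5; 1-month mean at 20% or 50% of the 6-month mean; error correlation between the two measures from 0 to 0.8 (in this set-up also the correlation of the individual changes); 15 complete pairs; the condition read as one volume measure plus creatine/water.

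**Step 1: the protocol's own figure.** Paired t-test, df = 14, noncentrality √15 × 1 = 3.873, one-sided critical value 1.761. Power is 97.9%, so the claim "with greater than 90% power on a one-sided test at the 5% level of statistical significance" is met.

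**Step 2: power of one planned ANOVA.** F with 2 and 28 df, critical value 3.340, noncentrality λ = 15 × Σ(mean at visit − overall mean)² / 0.5.
- Effect 1.0, 1-month mean at 20%: means 0, 0.2, 1.0, overall 0.4; sum of squares 0.16 + 0.04 + 0.36 = 0.56; λ = 16.8; power 94.5%.
- Effect 1.0, 1-month mean at 50%: sum of squares 0.25 + 0 + 0.25 = 0.50; λ = 15; power 91.7%.
- Effect 0.5: the sums shrink by 0.25 to 0.14 and 0.125; λ = 4.2 and 3.75; power 39.4% and 35.7%.

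With uncorrelated measures the chance that both are significant is the product: 0.945² = 0.89 and 0.917² = 0.84 at effect 1.0; 0.394² = 0.16 and 0.357² = 0.13 at effect 0.5.

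**Step 3: both ANOVAs significant, correlations 0 to 0.8** (simulation, 20,000 runs per setting).

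| Volume effect | Creatine/water effect | Chance the analysis is triggered |
|---|---|---|
| 1.0 | 1.0 | 84-91% |
| 0.8 | 0.8 | 56-73% |
| 0.6 | 0.6 | 24-43% |
| 1.0 | 0.5 | 33-40% |
| 0.5 | 0.5 | 13-29% |
| 0.3 | 0.3 | 2-10% |
| 1.0 | 0 | 4-5% |

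The last row shows the problem most clearly. Even when the individual changes correlate at 0.8, the analysis is triggered in about 1 study in 20, because creatine/water has no average change. Requiring both volumes to be significant could only lower these chances.

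**Step 4: effect on finding a real link.** Assume a true correlation of 0.7 and, for simplicity, two-sided paired t-tests as the condition (40,000 runs). An unconditional test of the correlation succeeds in 88% of studies. Under the condition, the share in which it is both run and significant is 80% at effects 1.0/1.0, 37% at 1.0/0.5, 25% at 0.5/0.5 and 3% at 1.0/0. At a true correlation of 0.5, the unconditional test itself succeeds in only about 50%.

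**Step 5: precision without the condition.** Fisher z with n = 15 has half-width 1.96/√12 = 0.566. For an observed r = 0.5, z = 0.549, limits −0.016 and 1.115, giving a 95% CI of −0.02 to 0.81. For r = 0.7, z = 0.867, giving 0.29 to 0.89.

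**The case against.** The strongest reply is that at the protocol's own delta/sigma=1 for both measures the condition is usually met: 84-91% by the planned ANOVA, 92% by paired t-tests with a correlation of 0.7. Under the ANOVA the analysis is then skipped in only about 9-16% of studies. That stands, and a flat statement that the link will often go unexamined would be wrong. It is not a full answer, because section 9.1 gives that effect as what 15 patients can detect, not as what is expected, and section 5.1 says the sample size was set on feasibility.

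A reader might also infer that the rule blocks the study's main mechanistic work or contradicts the secondary objectives. The documents support neither. The biopsy work (section 7.2) and secondary objectives c to e are not subject to the condition. No objective names the pairing of muscle volume with creatine/water, and objective e is itself worded around changes that have been noted. At most, the rule sits oddly beside those objectives.

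The sentence does not forbid descriptive exploration when the condition fails, and the closing sentence of section 2.4 promises a look at individual data. This stands in part. The scope of that sentence is unclear, since it follows the exploratory endpoints, and section 9.2 commits to the analysis only when both changes are significant. Nor is this detail that can be left to a separate analysis plan: the protocol states the rule.

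Finally, sample size limits the answer more than the rule does. Step 5 bears that out, and the pilot caveat in section 9.2 acknowledges it. But a small sample is a reason to give an estimate with its interval, not to filter on two significance tests.

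**Conclusion.** The concern holds for one analysis, the link between muscle volume change and creatine/water change. The condition tests the wrong thing and makes reporting depend on the results. How often it bites depends on effects the protocol does not state: rarely if both are as large as delta/sigma=1, in more than half of studies once both are about 0.6 or less, or if volume changes by 1.0 and creatine/water by only 0.5, and nearly always if creatine/water has no average change. These figures rest on the assumptions listed with the calculation and on 15 complete pairs. Section 6.8 does not replace dropouts after baseline and lets participants decline procedures, so there may be fewer.

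Priority is low to moderate. This is an exploratory step in a pilot, and the primary analysis is unaffected.

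**What to change.** Replace the conditional sentence in section 9.2 with something like: *In all participants with paired data, and whatever the significance of the mean changes, the association between individual baseline-to-6-month changes in soleus creatine/water and in muscle volume will be reported as an exploratory analysis, separately for the lower leg (where the soleus lies) and the upper leg, as a correlation coefficient with 95% confidence interval and a scatter plot.* Keep the caveat about pilot size.

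The cost is one sentence, a short table and two plots. Both measures are already scheduled at every imaging visit, so no scan, visit or patient is added. The small downside is an extra exploratory estimate for each volume, with a wide interval that should not be over-read. The CRP and serum creatinine analyses need no change, because section 9.2 does not place this condition on them.

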11.1 Safeguarding confidentiality

Personal data will be regarded as strictly confidential. To preserve anonymity, any data and laboratory samples leaving the site will identify participants by their initials and a unique trial identification code only. The trial will comply with the UK Data Protection Act, 2018. All trial records and Investigator Site Files will be kept at site in a locked filing cabinet with restricted access.

11.2 Long term data storage

At the end of the trial, Case Report Forms and Consent Forms will be securely archived for 5 years following publication of the last paper or report from the trial, in line with Sponsor policy and Standard Operating Procedures. This will allow any queries or concerns about the data, conduct or conclusions of the trial to be resolved.

12 Insurance and Finance

The Newcastle upon Tyne Hospitals NHS Foundation Trust has liability for clinical negligence that harms individuals toward whom they have a duty of care. NHS Indemnity covers NHS staff and medical academic staff with honorary contracts conducting the trial for potential liability in respect of negligent harm arising from the conduct of the trial. The Newcastle upon Tyne Hospitals NHS Foundation Trust is Sponsor and through the Sponsor, NHS indemnity is provided in respect of potential liability and negligent harm arising from trial management. Indemnity in respect of potential liability arising from negligent harm related to trial design is provided by NHS schemes for those protocol authors who have their substantive contracts of employment with the NHS and by Newcastle University Insurance schemes for the management of the study and for those protocol authors who have their substantive contract of employment with Newcastle University. This is a non-commercial trial and there are no arrangements for non-negligent compensation.

13 References

i who.int/chp/topic/rheumatic/en/

ii Roubenoff, R, Rall, LC. Humoral mediation of changing body composition during aging and chronic inflammation. Nutr Rev 1993; 51: 1–11

iii Greenlund LJ, Nair KS. Sarcopenia-consequences mechanisms and potential therapies. Aging. 2003;124:287–99

iv Roubenoff R, Rall RC. Rheumatoid Cachexia: metabolic abnormalities, mechanisms and interventions. Rheumatology. 2004;43:1219–23

v Roubenoff R, Roubenoff RA, Cannon JG, Kehayias JJ, Zhuang H, Dawson-Hughes B, et al. Rheumatoid Cachexia: Cytokine-driven Hypermetabolism Accompanying Reduced Body Cell Mass in Chronic Inflammation. J Clin Invest. 1994;93:2379–86

vi Anne Tournadre, Bruno Pereira, Fréderic Dutheil, et al. Changes in body composition and metabolic profile during interleukin 6 inhibition in rheumatoid arthritis J Cachexia Sarcopenia Muscle. 2017 Aug; 8(4): 639–646. Published online 2017 Mar 18. doi: 10.1002/jcsm.12189 PMCID: PMC5566648

